### 3.2.3. Profile of Previous Experience With ALKS 8700

#### 3.2.3.1. Clinical Studies

Five Phase I studies to evaluate the safety, tolerability, and pharmacokinetics (PK) of ALKS 8700 in healthy adults (ALK8700-001, ALK8700-A102, ALK8700-A103 and ALK8700-A104, ALK8700-A105) have been completed. Three Phase 1 studies (ALK8700-106, ALK8700-107, and ALK8700-A109) have been clinically completed and the data analyses are ongoing.

The general PK characteristics for ALKS 8700 have been evaluated in the abovementioned completed Phase 1 studies. ALKS 8700 undergoes rapid presystemic hydrolysis to MMF with a dose proportionate increase in MMF exposure over the ALKS 8700 dose range tested (49 to 980 mg; ALK8700-001). Administration of ALKS 8700 420 mg with a high-fat, high-calorie meal delayed absorption of MMF, resulting in a significant decrease in  $C_{max}$  (44%) and a modest reduction in area under the plasma concentration versus time curve calculated using the trapezoidal method from time zero to the last observed concentration above the lower limit of quantification (AUClast 11%, ALK8700-A102). Minimal accumulation of MMF was observed in plasma following repeated administration of 210 to 630 mg BID for 5 days (ALK8700-A102). In addition, RDC-6567 has been identified as a major human metabolite of ALKS 8700 that is primarily eliminated in urine (ALK8700-A105).

The relative bioavailability of ALKS 8700 462 mg compared with DMF 240 mg was initially evaluated in a fasted condition (ALK8700-A103) as well as in the presence of a high-fat, high-calorie meal (ALK8700-A104). ALKS 8700 462 mg resulted in similar MMF exposure to DMF 240 mg under fasted conditions and met the PK criteria for bioequivalence to DMF based on  $C_{max}$  and AUC (ALK8700-A103). ALKS 8700 462 mg resulted in similar MMF exposure to DMF 240 mg with a high-fat, high-calorie meal and met the PK criteria for bioequivalence to DMF for AUC, but  $C_{max}$  was 26% lower for ALKS 8700 as compared to DMF (ALK8700-A104).

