#### **7.7.1.2. Disallowed Concomitant Therapy**

Immunomodulatory treatments for RRMS (besides study treatment) are prohibited during treatment with study treatment unless approved by the Medical Monitor. Prohibited immunomodulatory therapies include, but are not restricted to the following:

- Any alternative drug treatments directed toward the treatment of MS such as chronic immunosuppressant therapy or other immunomodulatory treatments (including, but

CONFIDENTIAL

The information contained herein may not be used, disclosed, or published without the written consent of Biogen MA Inc.

not limited to: IFN-beta, IFN-alpha, glatiramer acetate, DMF, natalizumab, cyclophosphamide, methotrexate, azathioprine, teriflunomide, and fingolimod)

- Of note, the timing of discontinuing IFN-beta, IFN-alpha, glatiramer acetate, or DMF prior to initiating treatment with study treatment (Visit 2) is at the Investigator's discretion
- The initiation of a DMT for the treatment of RRMS is permitted if initiated after the last dose of study treatment (it is also preferable that it be initiated at least 1 day after Visit 15 and not on Visit 15)
- Any investigational product, including investigational symptomatic therapies for MS and investigational therapies for non-MS indications
- Total lymphoid irradiation, cladribine, T-cell or T-cell receptor vaccination, any therapeutic monoclonal antibody, mitoxantrone, cyclosporine, IV immunoglobulin, plasmapheresis, or cytapheresis

The use of corticosteroids for the treatment of clinical relapses and steroids that are administered by nonsystemic routes (e.g., inhaled or topical) are permitted.

Symptomatic therapy, such as treatment for spasticity, depression, or fatigue is not prohibited but should be optimized as early as possible after screening in an attempt to maintain consistent treatment during the study.

Immunization using inactivated, killed, or viral particle vaccines (e.g., influenza vaccine) is permitted and can be administered according to Investigator judgment. Vaccines using live or attenuated viruses should not be administered unless approved by the Medical Monitor.

Subjects should be instructed not to start taking any new medications, including nonprescribed drugs, unless they have received permission from the Investigator.

See Section [7.7.1.1](#) for details regarding the concomitant medication review.

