1.2. Summary of the Study Design

This is a multicenter open label study to evaluate the long-term safety and tolerability of ALKS 8700 administered up to 96 weeks for the treatment of RRMS. The target population for this study will be adults, aged 18 to 65 years, diagnosed with RRMS.

Subjects will enter into the study in one of two ways:

1. De Novo Subjects: Those who have not participated in any prior eligible study of ALKS 8700
2. Rollover Subjects: Those who have completed the treatment period for any prior eligible study of ALKS 8700

De Novo Subjects will be initially evaluated for eligibility at screening (Visit 1) that may last up to 21 days prior to Visit 2. For Rollover Subjects, Visit 2 will be the first visit of the study and there will not be a separate screening visit. For these subjects, Visit 2 of this study will occur at the time of or within 7 days of the subject's end of treatment visit in the antecedent study. Completed assessments taken at the end of treatment visit of the antecedent study will be carried forward and do not need to be repeated at Visit 2 of this study unless otherwise specified in the schedule of assessments [Table 1](#). At Visit 2, all eligible, consenting subjects will begin open label treatment. Any subject not currently receiving ALKS 8700 or DMF will initiate treatment with ALKS 8700 231 mg twice daily on Day 1 through Day 7 followed by 462 mg twice daily from Day 8 onwards. For those subjects already receiving ALKS 8700 or DMF prior to Day 1, the initial ALKS 8700 dose will be 462 mg twice daily starting from Day 1.

Study drug includes ALKS 8700 231 mg administered as one capsule and ALKS 8700 462 mg administered as two, 231 mg capsules. Capsules will be administered orally, twice per day. Study staff will administer the first dose of ALKS 8700 at Visit 2 (Day 1). From that point on during the treatment period, the staff will dispense ALKS 8700 for subjects' self-administration. Subjects will be instructed to take study drug with or without food.

Starting on Day 8 of treatment, dose reduction to ALKS 8700 231 mg twice daily is permitted at the investigator's discretion for subjects who are unable to tolerate ALKS 8700 462 mg twice daily. Once a subject has stabilized after dose reduction, attempts should again be made to

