⁸ Serology testing includes hepatitis B surface antigen, hepatitis C antibody, and human immunodeficiency virus antibody

⁹ Urinalysis includes urine dipstick, urine microscopy (as applicable), urine beta-2-microglobulin, urine albumin, and urine creatinine

¹⁰Vital sign measurements include temperature, respiratory rate, blood pressure, and heart rate. Blood pressure, respiratory rate, and heart rate will be measured after the subject has been in a seated or supine position for at least 5 minutes

¹¹Pharmacokinetic samples will be collected in a subset of de novo subjects at selected sites. Samples will be collected pre-dose, and at 0.5, 1, 2, 3, 4, 6, and 8 hours after the morning dose on Days 1 and 29. Additional PK samples will be collected prior to and approximately 2-3 hours following the morning or evening dose on Days 15 and 57. Specifics of study visits where PK samples will be collected and PK sampling procedures will be provided to the study sites outside of this protocol.

¹⁴Use "Screening" version at screening; use "Since Last Visit" version at all other scheduled timepoints

¹⁵At Visit 2, dispense Emergency Treatment Card to De Novo Subjects and confirm possession/redispense if necessary for Rollover Subjects. At all other visits, confirm subject's possession of card and redispense if necessary

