3.7. Pharmacokinetic Data Analysis

PK analyses will be performed using the PK analysis set. Individual plasma concentrations will be listed by actual sampling times and summarized by nominal sampling times using descriptive

statistics. Plots of individual and mean concentrations over nominal time will also be generated. PK parameters will be calculated using non-compartmental analysis. Parameters will be estimated using actual elapsed time from dosing, and summarized using descriptive statistics. A subject listing of individual PK parameters will be provided.

Non-compartmental analysis will be performed to estimate the PK parameters as data allow. Additionally, PK concentration data obtained from this study will may be combined with data from other studies to develop a population PK model, which will be reported separately.

The PK parameters to be calculated includes, but is not limited to:

- C_{\max} : Maximum observed concentration
- t_{\max} : Time to reach C_{\max}
- AUC_{last} : Area under the plasma concentration versus time curve calculated using the trapezoidal method from time zero to the last observed concentration above the lower limit of quantification.

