6.2. Handling Of Concentration Data Below The Lower Limit Of Quantification

For PK analysis, individual < LLOQ values will be converted using the following rules:

- < LLOQ values will be set to "0" if before t_{max} or
- < LLOQ values will be set to "missing" if after t_{max} For Tables and Listings:
- For individual concentration values, the < LLOQ values are considered equal to 0 for the calculation of descriptive statistics, but reported as '< LLOQ' in concentration listings.
- For mean concentration values, if the mean is < LLOQ, '< LLOQ' is reported in concentration tables.
- For mean concentration-related PK parameter values (eg, C_{max} , C_{last} , etc.), if the mean is < LLOQ, the mean of the value is reported in the PK tables.

For Figures:

- For individual and mean figures, < LLOQ values are presented as 0 before the last sampling time point (t_{last}) for the linear representation (no value for semi-log plot), and are not presented after t_{last} ,

During pharmacokinetic analysis, pre-dose values that are either missing or < LLOQ will be assigned a value of zero when calculating AUC values.

PK concentration values < LLOQ will be treated as zero for the determination of summary statistics and will be treated as missing for the calculation of the geometric means. For the presentation of summary statistics, if at least 1 subject has a concentration value < LLOQ for the time point, then the minimum value will be displayed as "< LLOQ". If more than 50% of the subjects have a concentration data value < LLOQ for the time point, then the minimum and

median values will be displayed as “< LLOQ”. If all subjects have concentration data values <LLOQ for the time point, then all order statistics (minimum, median, maximum) will be displayed as “<LLOQ”. If the mean is less than the lower limit of quantification, the mean values will be displayed as “<LLOQ”.

All original values will be presented in the by-subject listings.

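### SAP 6.2 turns a missing pre-dose concentration into zero on Day 29 as well as Day 1, and the only area named on Day 29 is a partial one that ends by 8 h

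*SAP*

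**What the plan says.** Full profiles are taken on two days. SAP 1.2 (Table 1, footnote 11) schedules a pre-dose sample and samples "at 0.5, 1, 2, 3, 4, 6, and 8 hours after the morning dose on Days 1 and 29"; the protocol's Table 1 gives the same times. Dosing is twice daily: "Capsules will be administered orally, twice per day" (SAP 1.2).

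SAP 6.2 states that "pre-dose values that are either missing or < LLOQ will be assigned a value of zero when calculating AUC values". It names no study day and makes no exception for subjects who already have drug on board.

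SAP 3.7 names one area, AUClast, calculated "using the trapezoidal method from time zero to the last observed concentration above the lower limit of quantification". The list is open ("The PK parameters to be calculated includes, but is not limited to"), but no other area is specified.

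Three facts in the protocol bear on this. MMF is also the active metabolite of DMF (3.3). Subjects already on DMF start ALKS 8700 without titration (5.2), and the investigator decides when DMF is stopped before Visit 2 (7.7.1.2). The analytes may include RDC-6567 and RDC-8439 as well as MMF (9.2).

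**The concern.** Zero is the right starting value for a first dose in a subject with no fumarate on board. It is also close to right for a sample that was measured and fell below the limit of quantification. It is not right for a sample that was never obtained from someone four weeks into twice-daily dosing, or from someone who took DMF until just before Day 1. In those cases the rule enters an invented number into the trapezoid as if it had been observed. Protocol 12.1 says results will rest on observed values. SAP 7 says missing values are not imputed unless indicated, and SAP 6.2 is where this imputation is indicated.

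The second issue concerns what the Day 29 area means. It is the only full profile after weeks of dosing, so readers will want to use it as exposure per dose. Sampling stops at 8 h, so it cannot serve that purpose for any analyte still present later. The 12-h concentration is nevertheless available in effect, because at steady state the measured pre-dose sample estimates it.

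**Working it through.** The documents give no AUC, half-life, trough or accumulation ratio, so there is no planned figure to reproduce. The two bounds in steps 1 and 2 and the factor in step 4 follow from the sampling times alone. All other percentages rest on assumed kinetics.

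**Inputs from the documents.** Sampling times 0, 0.5, 1, 2, 3, 4, 6 and 8 h; twice-daily dosing, taken as a nominal 12-h interval (the documents do not state 12 h); AUC by trapezoids.

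**Step 1: cost of the zero.** C0 enters only the first trapezoid, 0.5 × (C0 + C0.5)/2. Setting C0 to 0 removes 0.5/2 × C0 = 0.25 h × C0. For a flat profile the 0–8 h area is 8 h × C0, so the loss is 0.25/8 = 3.1%. If C0 is 10% of the mean 0–8 h concentration, the loss is 0.31%.

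**Step 2: cover of the interval.** In time, 8/12 = 66.7%. This is also the share of the area for a flat profile.

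**Step 3: illustration.** One-compartment model at steady state, 12-h interval, with assumed absorption rate 1.2/h and lag 0.75 h, read at the planned times:

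| Assumed half-life | Loss from C0 = 0 | Area to 8 h as share of true AUC0-12 |
|---|---|---|
| 1 h | 0.0% | 98% |
| 4 h | 1.0% | 80% |
| 12 h | 2.2% | 71% |
| 24 h | 2.7% | 69% |

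A wider grid (half-life 0.5–12 h, absorption rate 0.7 and 1.5/h, lag 0.5, 1.5 and 3 h) gives a loss from the zero of 0.0–2.8%. The trapezoid to 8 h is 66–111% of the true AUC0-12. The top of that range exceeds 100% because sparse samples around a sharp peak can overstate its area.

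For MMF, protocol 3.2.3.1 reports minimal accumulation. If that is read, as an assumption, as an accumulation ratio of at most 1.10, then 1/(1 − exp(−12k)) ≤ 1.10 gives k ≥ ln(11)/12 = 0.20/h and a half-life of at most 3.47 h. Over that part of the grid the loss from the zero is 0.0–1.9%.

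**Step 4: the two parts interact.** If AUC0-12 is formed by setting C12 = C0, the last trapezoid is 4 × (C8 + C0)/2, so C0 contributes a further 2 h × C0. Under the present rule a missing pre-dose sample would then remove 0.25 + 2 = 2.25 h × C0. In the step 3 model that is about 7% of AUC0-12 at a half-life of 4 h and 14% at 12 h; for a flat profile it is 2.25/12 = 18.8%. With the pre-dose sample present, AUC0-12 built this way is 93–111% of the true value over the wider grid.

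**The case against.** A reader might infer that the plan understates steady-state exposure. The documents do not support that. AUClast is correctly defined as running "from time zero to the last observed concentration above the lower limit of quantification", and neither document calls it steady-state or dosing-interval exposure. It falls short only if someone reads it as AUC0-12. Even then the direction is not fixed, since the trapezoid at these times can come out above the true 12-h area.

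A reader might also infer that the effect is large for the metabolites. The protocol says that "RDC-6567 has been identified as a major human metabolite of ALKS 8700 that is primarily eliminated in urine". That gives a route of elimination, not a rate. No half-life is given for any analyte, metabolites appear only as examples, and the PK population is defined by MMF.

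Other points for the plan also stand. The zero rule costs little and applies only where a sample is missing, and no missing rate is given. Nothing says that the PK subset includes anyone coming directly from DMF. The parameter list is open, and the data may feed a separate population PK model. PK is not among the listed study objectives or endpoints.

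These arguments limit the size of the problem. They do not make zero a correct value for an unobtained Day 29 trough.

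**Conclusion.** The point holds as a low-severity correction. The pre-dose rule in SAP 6.2 gives a wrong value when the sample is missing on Day 29, or on Day 1 in a subject coming directly from DMF. The error is 0.25 h × C0 in each affected profile. It is near zero for a rapidly cleared analyte and bounded at about 3.1% for a flat profile. Zero remains acceptable for a measured value below the limit of quantification.

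Separately, the Day 29 AUClast is a valid partial area ending no later than 8 h. It does not measure exposure over the nominal 12-h interval, and the documents do not allow the size or direction of the difference to be stated. The percentages between the bounds depend on the assumed half-lives, absorption rates and lags. The analysis is descriptive, in about 50 subjects, with no test attached.

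**What to change.** **SAP 6.2.** Limit the missing-equals-zero rule to Day 1 in subjects not coming from DMF. Elsewhere keep a missing pre-dose value missing. A trapezoid from time zero needs a starting value, so say in the same place whether AUClast is then omitted for that profile or how it starts. Leave the rule for measured values below the limit of quantification as it is.

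**SAP 3.7.** Label the Day 29 area as ending at 8 h. Add a Day 29 AUC0-12 that uses the measured pre-dose concentration as the 12-h value, and do not report it when the pre-dose sample is missing. Make both changes together: adding AUC0-12 under the present zero rule would raise the loss from 0.25 to 2.25 h × C0.

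**Cost.** A few sentences and one extra parameter from samples already planned. The downside is that C12 = C0 assumes steady state and similar morning and evening doses. Dose reduction and return to the maintenance dose are allowed between Day 8 and Visit 4 (protocol 7.2), so subjects with a recent dose change before Day 29 should be flagged or left out of the AUC0-12 summary.

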2. SAMPLE SIZE CONSIDERATION

A sample size of approximately 1000 patients will contribute to the long-term safety experience of ALKS 8700 in subjects with RRMS, to provide sufficient patient exposure to meet the ICH guidance on the extent of patient exposures required to assess clinical safety for a new drug.

3. DATA ANALYSES

3.1. Study Population

The study population, defined as all enrolled subjects who receive at least one dose of ALKS 8700, will be divided into three enrollment groups for summarizing safety and efficacy data:

1. De Novo Subjects
2. Rollover Subjects who were in ALKS8700 treatment group
3. Rollover Subjects who were in DMF treatment group

3.1.1. Definitions of Analysis Populations (Analysis Sets)

3.1.1.1. Safety Population

The safety analysis set, defined as all enrolled subjects who receive at least one dose of ALKS 8700, will be used in the safety analyses.

3.1.1.2. Efficacy Population

The efficacy endpoints to assess treatment effect over time will be analyzed using data from the Full Analysis Set (FAS), defined as all subjects who receive at least one dose of ALKS 8700 and have had at least one post-baseline efficacy assessment.

3.1.1.3. Pharmacokinetic Population

The PK analyses will use the PK analysis set, defined as all subject who receive at least one dose of study drug and have at least one measureable concentration of MMF. Pharmacokinetic samples will be collected in a subset of approximately fifty de novo subjects at selected sites.

3.1.1.4. Subgroup Variables

Renal impact will be defined by baseline GFR as: normal ($\geq 90 \text{ mL/min/1.73m}^2$), mild ($60 \leq - < 90 \text{ mL/min/1.73m}^2$) and moderate – severe ($< 60 \text{ mL/min/1.73m}^2$).

Age subgroup will be defined as age < 55 and age ≥ 55 at baseline.

3.1.2. Disposition

Subject disposition will be summarized by enrollment group and overall in terms of the following:

- Subjects enrolled in the study
- Subjects in the safety population
- Subjects in the FAS population
- Subjects in the Pharmacokinetic Population

- Subjects who completed the treatment period
- Subjects who completed the study (treatment and follow up period)
- Subjects who discontinued from the study during the treatment period
- Subjects by the reason for early discontinuation

Percentages of disposition are based on the subjects in the Safety Population. Reason for early discontinuation will be as indicated on the disposition electronic case report form (eCRF). A listing of disposition will be provided for all subjects.

3.1.3. Protocol Deviations

Subjects with major protocol deviations in the following categories will be summarized and listed by enrollment group and overall for each category as listed below:

- Did not meet the inclusion/exclusion criteria
- Received prohibited medications
- Non-compliant with study medication, as defined by subjects taking less than 70% or more than 105% of the protocol specified amount of study medication
- Other major protocol deviations

3.2. Demographics and Baseline Characteristics

For De Novo Subjects and Rollover Subjects who were in DMF treatment group in ALK8700 A302, demographics and baseline characteristics data will be collected at Visit 2. For Rollover Subjects who were in ALKS 8700 treatment group, these data will be carried over from information recorded in the antecedent ALK8700-A302 study unless otherwise specified.

Demographic data, including age, age category (18-19, 20-29, 30-39, 40-49, 50-55, and ≥ 55), as well as < 40 , ≥ 40), gender, race, weight, body mass index (BMI), ethnicity and region (US, non-US) will be summarized by enrollment group and overall.

Baseline disease characteristics will also be summarized by enrollment group and overall, using descriptive statistics. These include years since disease (MS) onset, years since diagnosis, number of relapses in the past 12 months, prior Disease modifying therapy, baseline Expanded Disability Status Scale (EDSS) scores and EDSS score category (0, 1-1.5, 2-2.5, 3-3.5, 4-4.5, and ≥ 5).

Medical history will be summarized by enrollment group and overall for the Safety Population. Demographic, baseline characteristics and medical history listings will be provided for all subjects.

3.3. Prior and Concomitant Medications

Prior medications are defined as medications taken prior to the first dose of the study medication (i.e., medications with a stop date prior to the first date of study drug in the current study). Concomitant medications are defined as medications taken during the period between the first dose date and the last dose date of study drug, inclusive. Post-discontinuation medications are defined as medications taken after the last dose of study drug. All medications as documented by the investigator will be coded using the World Health Organization Anatomical Therapeutic Chemical (WHO-ATC) drug dictionary herbal enhanced version (2016, 1st quarter).

Prior and concomitant medications will be summarized by the preferred drug name for the Safety Population, by enrollment group and overall. If a subject has taken a prior or concomitant medication more than once, the subject will be counted only once for the medication. All reported medications will be presented in the subject data listing.

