3.6.2. Adverse Events

All adverse events (AEs) will be coded by System Organ Class and Preferred Term using the Medical Dictionary for Regulatory Activities MedDRA version 20.1 or higher. The verbatim term will be included in the AE listings.

AEs will be identified as emerging in the treatment period and the follow up period. During the treatment period, an AE will be considered as treatment-emergent AE (TEAE) if the event starts or worsens on or after the date of first dose of study drug in the current study. The Treatment Period is defined as the first dose start date to the date of end of treatment (EOT) in the current study, inclusive.

During the follow up period, post-discontinuation emergent AEs (PDEAEs), defined as AEs that started or worsened after date of the EOT visit, will be summarized. For PDEAEs, the greatest severity before or on the date of the EOT visit will be used as the benchmark for the comparison

of the AEs occurring during the follow up period. The Follow-up Period is defined as the period between the date of the EOT visit plus 1 day and the last study visit, inclusive.

An overview table, including number of subjects with TEAEs, serious AEs (SAEs), AEs leading to study discontinuation, study drug-related TEAEs, and PDEAEs will be provided. Adverse events leading to study discontinuation and SAEs leading to death will be summarized in the period when the discontinuation or death occurred.

The following summary tables will be provided for the treatment period by enrollment group and overall:

- TEAEs by System Organ Class and Preferred Term
- TEAEs by System Organ Class, Preferred Term, and severity
- TEAEs by System Organ Class, Preferred Term, and relationship
- Study drug related TEAEs by System Organ Class and Preferred Term
- TEAEs experienced by $\geq 5\%$ of subjects by System Organ Class and Preferred Term
- SAEs by System Organ Class and Preferred Term
- AEs leading to study discontinuation by System Organ Class and Preferred Term
- Adverse Events of Special Interest by System Organ Class and Preferred Term

In addition, an AE overview table and AEs by System Organ Class and Preferred Term for PDEAEs during the Follow-up Period will be provided.

All AE tables will be sorted by System Organ Class and then Preferred Term in decreasing frequency based on all subjects in the Safety Population.

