3.8. Statistical Considerations for COVID-19

Due to the Coronavirus Disease 2019 (COVID-19) public health emergency, many data collection challenges arose in this study. However, additional efforts were made to collect more data related to COVID-19, including but not limited to protocol deviations, AEs for COVID-19, COVID-19 testing and vaccine for COVID-19, concomitant medication to treat COVID-19 AEs and vaccines to prevent COVID-19, and treatment and study discontinuation due to COVID-19 etc.

The impact of COVID-19 will be evaluated for the safety population. Data for subjects who discontinued the study due to COVID-19 will be summarized with the reason for discontinuation in the listing. An overview table, including the number of subjects with TEAEs, serious AEs (SAEs) related to COVID-19, will be provided by enrollment group and overall. All AEs related to COVID-19 will be included in the listings. COVID-19 related concomitant medication data will be summarized and included in the listings. Major protocol deviations related to COVID-19 will be provided in the listings. The protocol deviations log may be used to summarize the impact of COVID-19 in this study.

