5. CHANGES IN CONDUCT OR PLANNED ANALYSES FROM THE PROTOCOL

COVID-19 impact will be assessed and summarized for major protocol deviation, AE, concomitant medication, and subject disposition.

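### SAP 3.3 fixes medication coding to a 2016 WHO drug dictionary release, which cannot hold preferred names for the COVID-19 vaccines that fall within the planned medication summaries

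*SAP*

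**What the plan says.** SAP 3.3 sets the coding rule without exception: "All medications as documented by the investigator will be coded using the World Health Organization Anatomical Therapeutic Chemical" system, in the "drug dictionary herbal enhanced version (2016, 1st quarter". The same section sets the level of the table: "Prior and concomitant medications will be summarized by the preferred drug name for the Safety Population", by enrollment group and overall. Nothing there allows a later release.

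SAP 3.8 lists the extra data gathered because of the pandemic, including "concomitant medication to treat COVID-19 AEs and vaccines to prevent COVID-19". It then commits to an output: "COVID-19 related concomitant medication data will be summarized and included in the listings". SAP 5 repeats this as a change from the protocol: "COVID-19 impact will be assessed and summarized for major protocol deviation, AE, concomitant medication, and subject disposition".

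The adverse event dictionary is handled differently. SAP 3.6.2 codes with the "Medical Dictionary for Regulatory Activities MedDRA version 20.1 or higher", which leaves room for updating.

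**The concern.** The drug dictionary release predates the disease that SAP 3.8 was written to cover. A preferred drug name comes from the dictionary, so a product that is absent from the release has no preferred name of its own. Someone following SAP 3.3 exactly has two choices for a COVID-19 vaccine record: leave it uncoded, or assign an older and less specific term. Either way, the preferred-name table does not show COVID-19 vaccines as what they are. Concomitant medication is also one of the four items that SAP 5 names for assessing the impact of COVID-19, so a committed summary depends on records that the stated coding rule cannot handle properly.

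**Working it through.** No arithmetic applies. The check sets the sections side by side.

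1. **Release.** SAP 3.3 names one release, first quarter of 2016. It has no wording for later versions, and no other section of the SAP or protocol supplies any.

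2. **Scope.** SAP 3.3 applies that release to all medications the investigator documents. Protocol 7.7.1 defines concomitant therapy as any drug or substance given from enrollment to Visit 16, which takes in vaccines. SAP 3.8 itself groups vaccines with concomitant medication in the passage quoted above.

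3. **Level of summary.** The table in SAP 3.3 is by preferred drug name, so an entry depends on what the dictionary contains.

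4. **Dates.** SAP 3.8 identifies the disease by year: "Due to the Coronavirus Disease 2019 (COVID-19) public health emergency, many data collection challenges arose in this study". A release from early 2016 is earlier than a disease named for 2019, so it cannot hold a preferred name for a vaccine against that disease. This follows from the SAP's own dates and needs no outside source.

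5. **Which records.** SAP 3.3 defines concomitant as taken from first to last dose, inclusive. The coded concomitant table is therefore affected for COVID-19 vaccines given in that interval. A vaccine given only after the last dose counts as post-discontinuation, and no summary table is planned for that class.

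6. **Comparison.** The MedDRA rule is a minimum version, while the drug dictionary rule is a fixed one. The likeliest explanation is that SAP 3.8 was added without a matching update to SAP 3.3.

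For COVID-19 vaccines, the coding rule in SAP 3.3 and an informative preferred-name summary cannot both be achieved as written.

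**The case against.** The strongest reply is that this is a stale version label that loses no data. SAP 3.8 does not say that its COVID-19 medication summary must be by preferred name. Protocol 7.7.1.1 records the name, dates and indication of every medication, so COVID-19 records can be found and counted without a code. SAP 3.3 lists all reported medications. The dataset and programming specifications and the mock tables are separate documents (SAP 6, 8 and 9) and may name a later release.

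Most of this stands, and it limits the harm to coded tables. It does not remove the error. SAP 3.3 states the release itself and does not defer the choice to another document. If a later release was in fact used, the SAP misdescribes the method and still needs correcting.

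A reader might also infer four stronger things that the documents do not support:

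- **That COVID-19 treatments as a class cannot be coded.** SAP 3.8 names no treatment. They may be ordinary medicines already present in a 2016 release.
- **That the protocol deviation table is compromised.** SAP 3.1.3 has a category for prohibited medications but does not tie it to drug codes. Protocol 7.7.1.2 defines prohibited drugs largely by class, and SAP 3.8 refers to a separate deviations log.
- **That the reading of post-treatment safety is distorted.** SAP 3.3 plans no summary table of post-discontinuation medications, and neither document identifies an MS drug as introduced after early 2016.
- **That a large number of subjects is affected.** A count would need the share still on treatment when vaccines became available and the share vaccinated. The documents give neither.

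**Conclusion.** The point holds for COVID-19 vaccines. The coding rule is wrong as written, because it names a release that cannot code records the SAP expects to summarize. The firm statement of size is that any COVID-19 vaccine record coded under SAP 3.3 is uncoded or carries a non-specific term; the number of subjects is unknown. No efficacy endpoint, adverse event endpoint or analysis population is touched. Severity is minor.

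This rests on two readings: that vaccines count as medications under SAP 3.3, which Protocol 7.7.1 and SAP 3.8 support, and that the SAP text is the operative rule, since the separate specifications are not available here.

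**What to change.** In SAP 3.3, replace the fixed release with the WHO drug dictionary release in force at final database lock, for example worded as 2016 Q1 or later to match the MedDRA rule in SAP 3.6.2. Apply one release to the whole final database, recoding earlier records, and state that release in the report.

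The cost is one phrase in the SAP and a routine dictionary update. SAP 4 notes that interim analyses were planned for regulatory submission, so some preferred names may differ between interim and final outputs. A short note in the report would cover this.
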